4.4.4. Subject Global Aesthetic Improvement Scale

The S-GAIS rating will be obtained from the subject’s assessments of eligible buttock(s). If both the buttocks are eligible then S-GAIS will be evaluated separately for each buttock (left and right).

- **2-level S-GAIS Responder** is defined as a subject with S-GAIS rating of at least 2 (ie, 2, or 3) at an evaluation time point.
- **1-level S-GAIS Responder** is defined as a subject with S-GAIS rating of at least 1 (ie, 1, 2, or 3) at an evaluation time point.

4.4.5. Subject Satisfaction with Cellulite Treatment Assessment

The subject satisfaction with cellulite treatment rating will be obtained from the subject’s assessments of eligible buttock(s). If both the buttocks are eligible then assessment will be evaluated for two buttocks.

- A responder is defined as subjects with a response of “Satisfied” or “Very Satisfied” in the subject satisfaction with cellulite treatment assessment during evaluation.

4.4.6. Subject Self-Rating Scale

The SSRS rating score is obtained from the subject’s assessments of eligible buttock(s). If both the buttocks are eligible then assessment will be evaluated for two buttocks.

- A 1-Level SSRS responder is defined as a subject with at least slightly satisfied (ie, slightly satisfied [4], very satisfied [5] or extremely satisfied [6]) with her appearance of the cellulite on her buttocks during evaluation.
- A 2-Level SSRS responder is defined as a subject with at least very satisfied (ie, very satisfied [5] or extremely satisfied [6]) with her appearance of the cellulite on her buttocks during evaluation.

4.5. Safety Parameters

4.5.1. Adverse Events

Adverse event verbatim terms as reported by the investigator will be mapped to System Organ Class (SOC) and Preferred Term (PT) using Medical Dictionary for Regulatory Activities (MedDRA). The MedDRA version to be used in this study will be defined in the Data Management Plan (DMP).

4.5.1.1. Adverse Events during 180 Day Observation Phase

All AEs recorded from the day of screening (on or after Day 71/EOS of double-blind study) until they attain the Open-label Period study visit and any ongoing AEs from EN3835-302/303 studies at the time of screening (on or after Day 71/EOS of double-blind study) will be summarized. All changes in medical history occurring between completion of study EN3835-302/303 and the Screening Visit of study EN3835-304 will be considered AEs.

4.5.1.2. Adverse Events during Open-label Period

Adverse Event Categorization Before Retreatment

The AEs will be associated with time periods in the open label study period based on the start date of the AE compared to time period start date, as below:

- Start of Open-label Period – <Day 360 (M12)
- ≥Day 360 (M12) – <Day 540 (M18)
- ≥Day 540 (M18) – <Day 720 (M24)
- ≥Day 720 (M24) – <Day 1080 (M36)

Adverse Event Categorization after Retreatment

An AE will be associated with a treatment session during the retreatment session based on the start date of the AE compared to the date of the injections.

- AEs (which occur or worsen) with a start date between the Day 1 visit date and the day prior to the next dose or, if no further dose, the Day 71 visit date, will be associated with Treatment Session 1.
- If study drug is administered at the Day 22 visit, AEs (which occur or worsen) with a start date between the Day 22 visit date and the day prior to the next dose or, if no further dose, the Day 71 visit date, will be associated with Treatment Session 2.
- If study drug is administered at the Day 43 visit, AEs (which occur or worsen) with a start date between the Day 43 visit date and the Day 71 visit date will be associated with Treatment Session 3.
- AEs with a start date on or after Day 71 of retreatment will be aligned with observational assessment visits as, AE occurring in time period:
 - ≥Day 71 of retreatment – <Day 360 (M12)
 - ≥Day 360 (M12) – <Day 540 (M18)
 - ≥Day 540 (M18) – <Day 720 (M24)
 - ≥Day 720 (M24) – <Day 1080 (M36)

Refer to section [6.3.1.1](#) to identify AE time period status when the start date of an AE is unknown.

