3.1.1. Category I

- Subjects should have not received any collagenase treatments since the completion of the double-blind study.
- Subjects in which the maximum composite response was ONLY a 1-level composite improvement in cellulite severity at Day 71 as assessed by the PR-PCSS and CR-PCSS in either (or both) buttock(s) in the double-blind study. In cases where improvement was in both buttocks, the composite improvement of 1-level must have occurred in the same buttock (ie, the PR-PCSS and CR-PCSS improvement observed in the same buttock).
- Subjects who showed a 2-level improvement in one scale but only a 1-level improvement in the other scale, provided the composite improvement of 1-level was within the same buttock.
- Only buttocks with a composite 1-level improvement or less will be retreated.

- These subjects will be observed for time to reduction of response (defined in section 4.4.1) and safety approximately every 6 months for 2 years and will be observed annually for up to 3 years (Day 1080) from Day 71 of the double-blind study.

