3.1.3. Category III

- Subjects who received active study drug in study EN3835-302 or EN3835-303 but did not meet criteria to be included in Category I or II (ie, non-composite responders).
- Category III subjects will not be eligible for retreatment in this study.

Assessment of open-label efficacy following retreatment will be determined up to Treatment Visit 4 (Day 71 + 5 days), after which all subjects (including the subjects who did not accept the offer of re-treatment) will be observed for safety every 6 months for 2 years and annually for up to 3 years (Day 1080) after Day 71 of the double-blind study.

The study schema is provided in Figure 1 below:

Figure 1: Study Design

The Schedule of Events for all subjects up through 180 days following the double-blind studies is provided in [Table 1](#).

Table 1: Schedule of Events Up to 180 Days

Procedures^a	Screening A^b (≥Day 71 Visit of Double-blind Study) (+14 days)	Visit 1 Day 180^c (±14 days) M6/Early Termination	Durability Confirmation Visit^d
Unblinding of Investigator, subject and site to subjects' treatments in EN3835-302/303 ^e		X	
Informed consent ^f	X	X	
Inclusion/exclusion	X		
Digital photography	X	X	X
Prior/concomitant medications/procedures ^g	X	X	
Physical examination:	X		
• Body weight	X	X	
• Height	X		
Vital signs	X	X	
Collection of Samples			
• Clinical laboratory	X	X	
• Anti-AUX-I/anti-AUX-II antibody level	X		
• Pregnancy testing ^h	X	X	
Subject Cellulite Assessments			
• Review assessments' training and use materials	X	X	X
• Patient Reported Photonumeric Cellulite Severity Scale (PR-PCSS) ^{ij}	X	X	X
• Subject Global Aesthetic Improvement (S-GAIS) ⁱ	X	X	
• Patient Reported Cellulite Impact Scale (PR-CIS)	X	X	
• Subject Satisfaction With Cellulite Treatment Assessment	X	X	
• Subject Self-Rating Scale (SSRS)	X	X	
Investigator Cellulite Assessments			
• Review assessment's training and use materials	X	X	X
• Clinician Reported Photonumeric Cellulite Severity Scale (CR-PCSS) ^k	X	X	X
Assignment of Subject to Category I, II, or III ^l		X	
Local safety assessments ^m	X	X	X
Adverse events ⁿ	Monitored throughout study		

Table 1: Schedule of Events Up to 180 Days (Continued)

FOOTNOTES:

- ^a Unscheduled visits may be done as deemed necessary at any time during the study to ensure subject safety; assessments done at unscheduled visits are at the discretion of the investigator. No photographs or cellulite severity assessments will be done at unscheduled visits.

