- ^l Assignment of subjects to Categories will occur after unblinding of investigators, subject and site personnel to subjects' treatment in EN3835-302/303 and will depend on treatment and Day 71 cellulite severity improvements. Depending on the date of the database lock of the double-blind studies, assignments may occur at Day 180 Visit after assessments are completed or at a time thereafter during an unscheduled visit.
- ^m Local adverse events associated with the injection site, including acute (eg, erythema, bruising, pain, nodules/mass, ulceration, blistering, pruritus, swelling, and/or induration) and/or chronic (eg, skin thickening, fibrosclerosis, peau d'orange changes) cutaneous adverse events, will be recorded and evaluated for seriousness and severity.
- ⁿ Any AE that occurs between the completion of studies EN3835-302/303 and the Day 180 Visit will be reported and evaluated.
EFP=Edematous fibrosclerotic panniculopathy; EOS=End of study; M=Month(s).

The Schedule of Events beyond Day 180 for Category I and II and who are eligible and opted to receive retreatment is provided in [Table 2](#).

Table 2: Schedule of Events: Eligible Category I/II Subjects – Treatment Session Assessments

Procedures^a	Screening B^b (Day -14 to -1 relative to Tx Visit 1)	Tx Visit 1 Tx Session 1 Day 1	Tx Visit 2 Tx Session 2 Day 22 (±3 days)	Tx Visit 3 Tx Session 3 Day 43 (±3 days)	Tx Visit 4 End of Treatment Day 71 (+5 days)^c
Informed consent ^d	X				
Inclusion/exclusion	X				
Digital photography ^e	X	X ^f	X ^f	X ^f	X
Prior/concomitant medications/procedures ^g	X	X	X	X	X
Physical examination:	X				
• Body weight	X		X ^h	X ^h	X
• Height	X				
Vital signs	X	X ⁱ	X ⁱ	X ⁱ	X
ECG ^j	X				
Collection of Samples					
• Clinical laboratory	X				X
• Anti-AUX-I/anti-AUX-II antibody level	X		X	X	X
• Pregnancy testing ^k	X	X ^h	X ^h	X ^h	X
Subject Cellulite Assessments					
• Review assessments' training and use materials	X	X	X	X	X
• Patient Reported Photonumeric Cellulite Severity Scale (PR-PCSS) ^{l,m}	X	X	X	X	X
• Subject Global Aesthetic Improvement Scale (S-GAIS) ^l	X				X
• Patient Reported Cellulite Impact Scale (PR-CIS) ^l	X				X
• Subject Satisfaction With Cellulite Treatment Assessment ^l	X				X
• Subject Self-Rating Scale (SSRS) ^l	X				X
Investigator Cellulite Assessments					
• Review assessment's training and use materials	X	X	X	X	X
• Clinician Reported Photonumeric Cellulite Severity Scale (CR-PCSS)	X	X	X	X	X
Selection of dimples to be treated		X	X	X	

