AEs Before Retreatment: The new AEs recorded on or after Open-label Period starts but before retreatment in the open-label study will be summarized for subjects in Open-label Observation Population. This will include AEs of all Category I and II subjects recorded before retreatment and AEs of all Category III subjects.

An overall summary of new AE will be presented by subject category (ie, Category I, II, III, and Overall) and by time period as described in section 4.5.1.2, and will include:

- Any new AE
- Any new AE of special interest
- Any new serious AE

- Any new mild, moderate, and severe AE
- Any new AEs leading to study discontinuation
- Any new AEs resulting in death

The following summary tables will be presented by SOC and PT by subject category (ie, Category I, II, III, and Overall):

- All AEs
- AEs by Severity
- Serious AEs
- AEs leading to study discontinuation
- AEs resulting in death
- AEs of Special Interest

Serious and most common non-serious AE by order of frequency (Most frequent, 2nd most frequent and 3rd most frequent) will be summarized by PT. Most common non-serious AEs are any preferred term that at least 5% of the subjects reported at least once.

Subject listings of all AEs, serious AEs, AEs leading to study discontinuation, AEs resulting in death and AEs of Special Interest will be provided.

AEs During and after Retreatment: The new AEs recorded on or after retreatment in the open label study will be summarized for subjects in OLR Population. This will include AEs of all Category I and II subjects recorded after retreatment.

An overall summary of new AE and new AE related to study drug recorded after retreatment will be presented for each subject category (ie, Category I, II and Overall) by treatment sessions and time period (ie, all study periods and each study period as described in section 4.5.1.2), and will include:

- Any new AE
- Any new AE of special interest
- Any new serious AE
- Any new mild, moderate, and severe AE
- Any new AEs leading to study drug withdrawn/interruption
- Any new AEs leading to study discontinuation
- Any new AEs resulting in death

The following summary tables will be presented by SOC and PT by subject category (ie, Category I, II, and overall) and each treatment sessions [TX1, TX2, TX3, and Total ('Total' includes AEs reported during Treatment Session 1, 2, and 3, and Observation Period post Day 71 of retreatment)]:

- All AEs
- AEs by causal relationship to study drug
- AEs by Severity

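### By-period adverse event summaries set windows of unequal length side by side without time at risk, so the columns cannot be compared over time

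*SAP*

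**What the plan says.** **Periods before retreatment.** Section 4.5.1.2 of the SAP states: "The AEs will be associated with time periods in the open label study period based on the start date of the AE". There are four periods. The first runs from the start of the Open-label Period to before Day 360 and the second from Day 360 to before Day 540. The last two are "≥Day 540 (M18) – <Day 720 (M24)" and "≥Day 720 (M24) – <Day 1080 (M36)". The start of the first period varies: by a footnote to Table 1 (section 3.1.3), category "assignments may occur at Day 180 Visit after assessments are completed or at a time thereafter during an unscheduled visit".

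**Periods and sessions after retreatment.** AEs go first to treatment sessions that start on Days 1, 22 and 43. Those starting "between the Day 43 visit date and the Day 71 visit date will be associated with Treatment Session 3", and a session with no further dose runs on to Day 71. Later AEs go to a window from retreatment Day 71 to before Day 360, and then to the same later periods as above.

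**Visits.** Under section 3.1.1 (and likewise 3.1.2), subjects are seen "approximately every 6 months for 2 years and will be observed annually for up to 3 years". Section 3.1.3 has all subjects "observed for safety every 6 months for 2 years and annually for up to 3 years (Day 1080)".

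**Tabulation.** Section 7.7.2 gives the pre-retreatment overall AE summary by category and "by time period as described in section 4.5.1.2". After retreatment the overall summary is by session and period, and the tables by system organ class and preferred term are by session. The tables hold occurrences and numbers of subjects, and a subject counts once per term. Section 6.1 adds percentages. The only follow-up time summarised is overall time in study (section 7.1).

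**The concern.** The proportion of subjects with at least one AE in a window is a cumulative incidence, so it rises with the length of the window even when nothing about the risk changes. The number of occurrences rises in proportion to length. The last pre-retreatment period is twice as long as the two before it, and nothing in section 7.7.2 scales the figures to the time observed.

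Long-term safety is the first primary objective and safety of retreatment the second (section 2.1). There is no formal test, so the descriptive tables are the result. A reader who looks across the periods will be comparing quantities measured over different lengths of time.

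**Working it through.** The SAP states no AE rate, and its sample size of about 420 (section 3.6) is a rollover count, so there is no planned figure to reproduce. All incidences below are assumptions, shown over a range.

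**1. Nominal window lengths before retreatment** (section 4.5.1.2)

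- Start of Open-label Period to Day 360: at most 360 − 180 = 180 days, less if the period starts after Day 180
- Day 360 to 540: 180 days
- Day 540 to 720: 180 days
- Day 720 to 1080: 360 days

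Each window closes with one scheduled visit, so visit frequency falls from one per 180 days to one per 360 days.

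**2. Effect of length at a constant rate.** With incidence p in 180 days, everyone at risk throughout and complete capture, the 360-day incidence is 1 − (1 − p)².

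| Assumed p in 180 days | Shown in 360 days | Ratio |
|---|---|---|
| 2% | 4.0% | 1.98 |
| 5% | 9.8% | 1.95 |
| 10% | 19.0% | 1.90 |
| 20% | 36.0% | 1.80 |
| 40% | 64.0% | 1.60 |

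Occurrences double exactly.

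**3. What would cancel it.** With a fixed denominator, the last column matches the earlier ones if the fraction still observed is p ÷ [1 − (1 − p)²]. This is 0.505 at p = 2% and 0.625 at p = 40%, that is, a loss of about 37% to 50% of subjects. With an at-risk denominator, it cancels if AE capture in year 3 falls to half. The SAP gives neither quantity.

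**4. Windows after retreatment.** Retreatment Day 71 falls 70 days after the first injection.

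- Start at Day 180: 180 + 70 = 250, leaving 360 − 250 = 110 days in the first window. The last window is 360 ÷ 110 = 3.3 times as long. At a constant rate of 10% per 180 days, the first window shows 1 − 0.9^(110/180) = 6.2% and the last 19.0%.
- Start after about Day 360 − 70 = 290: the first window is empty.
- The SAP's own example (section 3.1.2) starts on Day 351 and ends on Day 421. Its first window is empty, and the next has 540 − 421 = 119 days rather than 180.

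**5. Sessions.** On schedule these last 22 − 1 = 21, 43 − 22 = 21 and 71 − 43 = 28 days, or up to 33 with the +5 days on Day 71. The ±3 days on Days 22 and 43 (Table 2) widen this to 18–24, 15–27 and 25–36 days. A first session with no further dose lasts about 70 days.

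At a constant rate, 20% in 21 days becomes 1 − 0.8^(28/21) = 25.7% to 1 − 0.8^(33/21) = 29.6% in 28 to 33 days. If onset after injection is instead exponential with an assumed median of 1 to 3 days, at least 1 − 2^(−21/3) = 99% of onsets fall within 21 days, and session length hardly matters.

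**6. Check of the remedy.** The rate is −ln(1 − p) ÷ 180 × 365.25 × 100 per 100 subject-years: 10.4 for p = 5% and 45.3 for p = 20%. It is the same in a 180-day and a 360-day window, so the ratio returns to 1.00.

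**The case against.** The SAP claims no trend. The tables are descriptive, the bounds are printed as days and months, and crude incidence by visit interval alongside listings is common practice. Before retreatment only the overall summary is by period; the tables by system organ class and preferred term are by category. The table shells are in a separate SAP module that is not at hand. All of this stands, and it makes the point one of interpretability, not of a false statement.

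A reader might infer that the third-year column will show a near doubling, or that a true halving of the rate would look flat. The SAP does not support so firm a reading. Section 6.1 gives two denominator rules (subjects in the population, and subjects with non-missing values), and section 7.7.2 does not choose between them for AE periods. With a fixed denominator, dropout would shrink the last column, and so would retreatment, which moves later AEs out of this table. Visits at half the frequency may also lower capture, though AEs are monitored throughout and every window still closes with one visit. The direction of the length effect is certain; the net figure is not.

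A reader might also infer that a rise at the third session is built in. The visit windows let the session lengths overlap, and for acute injection-site reactions the effect is close to nil. Length matters there mainly for later-onset events and for subjects with no further dose.

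**Conclusion.** The by-period AE summaries cannot be compared over time as planned. With an at-risk denominator, complete capture and a constant rate, the Month 24 to 36 column shows 1.6 to 2 times the incidence of a 180-day column, for assumed incidences of 40% down to 2% per 180 days, and twice the occurrences. Depletion and sparser visits act in the opposite direction by unknown amounts, so the crude figures cannot be corrected by eye. Halving the last column is no remedy either, because the first window starts at a different time for different subjects.

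The same holds after retreatment, where the first observation window ranges from about 110 days to none. The session comparison is a secondary matter. The change should be made because the tables serve the primary safety objectives and the SAP is where the summary measure is fixed.

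**What to change.** In section 7.7.2, add to each by-period overall AE summary the subject-years at risk, and the AEs and serious AEs per 100 subject-years.

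- **Before retreatment:** count time from the later of period start and Open-label start to the earliest of period end, first retreatment injection and last date in study.
- **After retreatment:** count time from the later of period start and retreatment Day 71 to the earlier of period end and last date in study. The Day 71 visit date now falls in both the last session and the first observation window; place it in one.
- **Sessions (secondary):** add subject-days from each injection to the day before the next dose, or to the Day 71 visit if there is none, and the AE rate per subject-time. Assign each AE to the most recent injection, so that none counts towards two sessions.

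The cost is a few extra table rows. First-injection date, AE start date and last date in study are already used in Table 17, so no new data are needed, and the planned counts and percentages can stay.

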 - ⁱ Up to 4 hours before injection; approximately 15 and 30 minutes after injection. Pulse and blood pressure to be taken after subject has been sitting for 5 minutes. Vital signs must be stable before the subject is discharged. Refer to section 14.9 of Protocol Amendment 3.
 - ^j Do not conduct if Screening B visit date is within 12 months of obtaining an ECG during the double-blind study (EN3835-302/303).
 - ^k Serum pregnancy test on Screening visit and Day 71/EOS visit; urine pregnancy test on Day 1, Day 22, and Day 43 visits and Unscheduled Visit.
 - ^l Assessment made via photographs (if treatment visit, use photographs taken before marking dimples and injection sites).
 - ^m Subject assessments should be completed independently and prior to investigator assessments at each visit. Includes bot buttocks regardless of treatment, each buttock should be assessed independently.
 - ⁿ At least one of the Category I subject’s buttocks must have scores/ratings of at least 2 in both the CR-PCSS and PR-PCSS to be eligible to receive treatment. Category II subjects must have at least a 1-level composite response reduction compared to Day 71 of the EN3835-302/303 study AND no longer maintain a 2-level composite response compared to baseline in the EN3835-302/303 study on either or both buttocks.
 - ^o Local adverse events associated with the injection site, including acute (eg, erythema, bruising, pain, nodules/mass, ulceration, blistering, pruritus, swelling, and/or induration) and/or chronic (eg, skin thickening, fibrosclerosis, peau d’orange changes) cutaneous adverse events, will be recorded and evaluated for seriousness and severity.
- ECG=Electrocardiogram; EFP=Edematous fibrosclerotic panniculopathy; EOS=End of study; Tx=Treatment.

The Schedule of Events beyond Day 180 for subjects in Category I and II who are eligible and opted to receive retreatment, for the subjects in Category II who are not eligible for retreatment, and Category I and II subjects who are eligible but opted not to have retreatment is provided in [Table 3](#).

Table 3: Schedule of Events: Category I/II Subjects – Observation Assessments

	OBS Visit 2 Day 360 (±30 d) (M12)	OBS Visit 3 Day 540 (±30 d) (M18)	OBS Visit 4 Day 720 (±30 d) (M24)	OBS Visit 5 Day 1080/EOS/Early Termination (±30 d) (M36)	Durability Confirmation Visit^b
Procedures^a					
Verification of informed consent	X				
Inclusion/exclusion	X				
Digital photography	X	X	X	X	X

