Prior/concomitant medications/procedures ^c	X	X	X	X	
Anti-AUX-I/anti-AUX-II antibody level	X	X	X	X	
Subject Cellulite Assessments					
• Review assessments’ training and use materials	X	X	X	X	X
• Patient Reported Photonumeric Cellulite Severity Scale (PR-PCSS) ^{d,e}	X	X	X	X	X
• Subject Global Aesthetic Improvement Scale (S-GAIS) ^d	X	X	X	X	
• Patient Reported Cellulite Impact Scale (PR-CIS) ^d	X	X	X	X	
• Subject Satisfaction With Cellulite Treatment Assessment ^d	X	X	X	X	
• Subject Self-Rating Scale (SSRS)	X	X	X	X	
Investigator Cellulite Assessments					
• Review assessment’s training and use materials	X	X	X	X	X
• Clinician Reported Photonumeric Cellulite Severity Scale (CR-PCSS) ^e	X	X	X	X	X
Local safety assessments ^f	X	X	X	X	X
Adverse events	Monitored throughout study				

FOOTNOTES:

- ^a Unscheduled visits may be done as deemed necessary at any time during the study to ensure subject safety; assessments done at unscheduled visits are at the discretion of the investigator. No photographs or cellulite severity assessments will be done at unscheduled visits.
- ^b If the composite (CR-PCSS and PR-PCSS) ratings worsen by at least 1-level composite response ratings for a subject, an additional visit should be scheduled 14 days (± 5 days) later to confirm reduction of response, via re-assessment with the CR-PCSS and PR-PCSS. If reduction of response is confirmed, subjects will be offered one course of retreatment (one and only one course of retreatment in up to 2 buttocks concurrently will be offered to an individual subject during this open-label study from Visit 1 to Visit 5 (approximately 6 to 36 months after Day 71 of the double-blind study, respectively). The Sponsor has

Table 3: Schedule of Events: Category I/II Subjects – Observation Assessments (Continued)

decided to terminate the EN3835-304 clinical trial at the completion of 3-year time point (Day 1080) and will offer voucher(s) for commercially approved Qwo redeemable only for those trial participant(s) who will miss their potential retreatment opportunity due to this decision. Retreatment will only be offered following confirmation of eligibility through cellulite assessments performed at the Day 1080 visit for those participants, and a confirmation visit (as applicable).

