6.3.1. Imputation of Partial Dates

6.3.1.1. Adverse Event Status for Completely Unknown AE Start Date

The following rules will apply in cases where start date of an AE is completely unknown before retreatment:

- If the AE onset date is unknown and the end date is on or after Day 71/EOS visit date of double-blind studies but before start of open-label period for the subjects who moved to open-label period OR end date is on or after Day 71/EOS visit date of double-blind studies for subjects who didn't enter open-label period, then the AE will be associated with 'Day 71/EOS Phase 3 – until start of open-label period.'
- If the AE onset date is unknown and the end date is on or after start of Open-label period but before M12 assessment date, then the AE will be associated with 'Start of Open-label period – Day 360 (M12)' period.
- If the AE onset date is unknown and the end date is on or after M12 visit date but before M18 assessment date, then the AE will be associated with 'Day 360 (M12) – Day 540 (M18)' period.
- If the AE onset date is unknown and the end date is on or after M18 visit date but before M24 assessment date, then the AE will be associated with 'Day 540 (M18) – Day 720 (M24)' period.
- If the AE onset date is unknown and the end date is on or after M24 visit date but before M36 assessment date, then the AE will be associated with 'Day 720 (M24) – Day 1080 (M36)' period.

The following rules will apply in cases where start date of an AE is completely unknown after retreatment:

- If the AE onset date is unknown and the end date is on or after Day 1 visit date but before Day 22 visit date, then the AE will be associated with Treatment Session 1.
- If the AE onset date is unknown and the end date is on or after Day 22 visit date but before Day 43 visit date, then the AE will be associated with Treatment Session 2.
- If the AE onset date is unknown and the end date is on or after Day 43 visit date but before Day 71 visit date, then the AE will be associated with Treatment Session 3.
- If the AE onset date is unknown and the end date is on or after Day 71 or ongoing, then the AE will be associated with the observation assessment and will be imputed as:
 - If the AE onset date is unknown and the end date is on or after Day 71 visit date of retreatment session but before M12 assessment date, then the AE will be associated with 'Day 71 – Day 360 (M12)' period.

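### The rules that assign adverse events to periods leave some events with no period and put others in two

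*SAP*

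**What the plan says.** **Known onset (SAP 4.5.1.2).** Events are placed by start date. The before-retreatment and after-retreatment lists both end with "≥Day 720 (M24) – <Day 1080 (M36"), and neither has a later period. After three retreatment doses, events "with a start date between the Day 43 visit date and the Day 71 visit date will be associated with Treatment Session 3". Sessions 1 and 2 also run to the Day 71 visit date if no further dose is given. The next rule reads "AEs with a start date on or after Day 71 of retreatment will be aligned with observational assessment visits".

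**Unknown onset (SAP 6.3.1.1).** The event goes to the period in which its end date falls. The last such period requires that "the end date is on or after M24 visit date but before M36 assessment date". After retreatment, a separate rule covers the case "If the AE onset date is unknown and the end date is on or after Day 71 or ongoing" and sends the event to observation. Partial onset dates are handled by month and year.

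**Follow-up (SAP Tables 3 and 4).** The last visit is "OBS Visit 5 Day 1080/EOS/Early Termination (±30 d) (M36"), with a local safety assessment. For Category I and II subjects whose composite ratings worsen, "an additional visit should be scheduled 14 days (± 5 days) later to confirm reduction of response", again with a local safety assessment. Table 3, footnote b, foresees this after the final visit too: "cellulite assessments performed at the Day 1080 visit for those participants, and a confirmation visit (as applicable").

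**Use (SAP 7.7.2).** The overall adverse event summaries before and after retreatment are given by these periods. After retreatment, the tables by system organ class and preferred term have a column for each session and a Total. All adverse event tables show numbers of occurrences as well as of subjects.

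**The concern.** A set of analysis periods should give every event exactly one place. These rules do not: some onset dates fit no period, one date fits two, and some ongoing events of unknown onset cannot be placed. A programmer must then either improvise or follow rules that omit some occurrences and assign others twice. Long-term safety and the safety of retreatment are primary objectives (SAP 2.1), and the by-period overview is where a reader looks to see when events arose. Subject counts need not add up across periods, but occurrence counts should.

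A secondary matter is direction. Because unknown-onset events follow their end date, an event that lasts to retreatment Day 71 or beyond is never placed in an injection session. Lasting local reactions such as skin thickening are among the events that SAP 3.11.1 says will be recorded.

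**Working it through.** The plan states no figure to reproduce. The check treats the rules as date intervals and asks, for each day, how many periods contain it.

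**1. Upper end**

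Inputs: the last period stops before Day 1080 (4.5.1.2); visit window ±30 days (Tables 3 and 4); confirmation visit 14 ± 5 days later (Table 3, footnote b).

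- Latest final visit: 1080 + 30 = Day 1110.
- Latest confirmation visit: 1110 + 14 + 5 = Day 1129.
- Nominal-day reading, to the latest final visit: 1110 − 1080 + 1 = 31 study days with no period.
- Nominal-day reading, to the latest confirmation visit: 1129 − 1080 + 1 = 50 study days. This applies to Categories I and II only, since Table 4 has no confirmation visit.
- Visit-date reading, in which Day 1080 means the actual Month 36 visit: the visit day itself, plus up to 14 + 5 = 19 days to a confirmation visit, so at most 20 days.

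The gap exists on either reading. In 6.3.1.1 an unknown-onset event ending on or after the Month 36 assessment likewise meets no rule.

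**2. Retreatment Day 71**

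The session rules end on the Day 71 visit date and observation starts on that same day. Going through every day after the first dose, Day 71 is the only one with two periods:

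| Doses given on | Periods containing Day 71 |
|---|---|
| Days 1, 22, 43 | Session 3 and observation |
| Days 1, 22 | Session 2 and observation |
| Day 1 only | Session 1 and observation |

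This takes the session range to include its end date. The SAP supports that: where it wants an earlier end, it says the day before the next dose.

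**3. Unknown onset**

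Before retreatment, every rule needs an end date, so an ongoing event has no period. After retreatment, an ongoing event reaches observation, but the sub-period rules again need an end date.

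Examples, assuming retreatment Day 1 is study Day 200 and the Month 36 visit is on Day 1080 (study day = 200 + retreatment day − 1):

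| True onset | End | If onset known | If onset unknown |
|---|---|---|---|
| Day 1 | Day 10 | Session 1 | Session 1 |
| Day 1 | Day 30 | Session 1 | Session 2 |
| Day 2 | Day 60 | Session 1 | Session 3 |
| Day 1 | Day 90 (study Day 289) | Session 1 | Day 71 to Month 12 |
| Day 43 | Day 80 (study Day 279) | Session 3 | Day 71 to Month 12 |
| Day 1 | ongoing | Session 1 | observation, no sub-period |
| Day 1 | Day 900 (study Day 1099) | Session 1 | none |

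The last row falls through because 1099 is past 1080.

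**The case against.** Several stronger inferences are tempting, and the SAP does not support them.

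- *Events are lost from the safety analysis.* They are not. Before retreatment, the tables by system organ class and preferred term are by subject category, not by period. After retreatment, the Total column takes in the observation period with no upper limit, the overview also covers all study periods together, and all events are listed.
- *Everything found at the final visit has no period.* Assignment is by start date. An event found there that began on Day 1000 is in the last period; only onset on or after the cut-off is uncovered.
- *Half of completers have on average 15 days of unassigned follow-up.* That needs final visits spread evenly over ±30 days, which is an assumption, and Day 1080 read as a nominal day. Section 6.3.1.1 works with actual visit and assessment dates, which undercuts the second condition. Section 7.7.2 specifies counts and not person-time rates, so uncovered time matters only if an event starts in it.
- *The unknown-onset rule contradicts a worst-case principle.* The SAP states that principle for missing severity, missing relationship and medication status, and never for period assignment. This is a different choice, not a contradiction. A blanket default to Session 1 would misplace events too, such as one that ended at Month 30.

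The defence also has two textual points. The lead-in to the before-retreatment list compares onset with the start of a period, so a programmer might place a late event in the last period begun; but the explicit upper limit says otherwise. And the description of the Total column speaks of observation after Day 71, which suggests that the session owns that day. The SAP nowhere says that such an event is counted twice. That helps to choose the fix, but leaves two assignment rules claiming the same date.

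**Conclusion.** The period rules in 4.5.1.2 and 6.3.1.1 are neither exhaustive nor mutually exclusive. Three defects stand on the text: no period for onset on or after the Month 36 cut-off, or for unknown-onset events ending on or after it; two periods for onset on the retreatment Day 71 visit date; and no period before retreatment, or no sub-period after it, for ongoing events of unknown onset.

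This is a minor point. It can omit or double-assign occurrences in the by-period and by-session summaries only. The SAP gives no event counts, so the number affected cannot be computed. It is probably small: the uncovered span is short against three years, the overlap is a single day per retreated subject, and wholly unknown onset should be rare given local assessments at every treatment visit and on Day 71. The overlap rests on reading the session range as including its end date. The shift of lasting unknown-onset events out of Sessions 1 to 3 is real but secondary, since the true session cannot be known.

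**What to change.** 1. In 4.5.1.2 (both lists) and 6.3.1.1, define the last period as Day 720 (Month 24) to end of study, and say whether period boundaries are nominal days or actual visit dates.
2. Give the Day 71 visit date to one period only. Starting observation on the following day agrees with how 7.7.2 describes the Total column.
3. Extend the unknown-onset rules to ongoing events, before and after retreatment, and name the sub-period.
4. Secondary: assign unknown-onset events to the earliest period compatible with what is known about them, or keep assignment by end date and show the earliest-period version as a sensitivity summary.

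The first three are wording changes at almost no cost. The fourth may raise session-level counts slightly and will place some late events too early, which is why a sensitivity summary is a reasonable alternative.
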